3.5.2. ANALYSES OF STUDY POPULATION

Analysis for primary and secondary endpoints will use the Per Protocol population, which consists of those cases with complete data for one or more of the primary endpoints collected per the protocol at the 22+ month follow-up visit (or, as described below in the section on Missing Data, at the last or next available visit if the primary endpoint in question is missing at the 24- month visit). The exception to this is the primary endpoint of Absence of Revision/Removal/UADE, which is cumulative; therefore all cases that have failed at or prior to 24 months due to a revision or UADE will be included in the analysis of that primary endpoint. For each primary endpoint, all available data will be used, even if the subject has missing data for one or more of the other endpoints. Since indications and inclusion/exclusion criteria are exactly the same for both device groups, and because randomization is received at the time of surgery, it is expected that few patients will fail to receive the assigned treatment. However, in the event that they do not, the primary analysis will use the device that was actually implanted if it was a study device; if a study device is not received, the patient will not be included in the primary analysis.

Bilateral patients will be used in the primary analysis for the of Radiographic Success and Absence of Revision/Removal/UADE endpoints, but will be analyzed separately for the Knee Society Function and Assessment endpoints. The bilateral patients will not be included in the primary analysis for the Knee Score endpoints, as there is no way to ensure that the knee scores for one knee will not be affected by the other. The sample size has been increased by 10% to allow for this, a percentage based on the bilateral enrollment in the post-approval study for the OxfordTM Menisal Unicompartmental Knee System.

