3.0 STATISTICAL ANALYSIS PLAN

This is a two-group, multi-center, randomized clinical trial to compare Biomet's cemented Oxford® Partial Knee System to another active intervention, the Oxford® Cementless Partial Knee System (abbreviations: Control vs. Cementless). Imbalanced, blocked randomization (2:1, Cementless vs. Control) will be implemented.

Randomization will be per patient. In the event that an intraoperative screen failure occurs post-randomization, randomization will not be reassigned and this patient will not count toward the overall sample size. Randomization will continue with the next subject enrolled as previously described. The randomization plan will be produced using SAS v 9.2 for Windows. Randomization will be by center, and each site will receive separate randomization plans using a predetermined block size that will remain undisclosed to the sites. The randomization assignments will be in the form of envelopes to be opened intra-operatively after the first tibial cut and bone quality is assessed against the eligibility criteria.

The primary study endpoint will consist of four (4) individual co-primary endpoints, including both safety and efficacy measures. The following endpoints are included as individual parts of the primary endpoint:

- 1. Knee Society Assessment Score number of points received for the Knee Society Assessment Score at the 22+ month assessment
- 2. Knee Society Function Score number of points received for the Function Score at the 22+ month assessment.
- 3. Revisions or removals of any component of the device or an unanticipated, device-related adverse event (UADE) at any time point. This is a binary endpoint in which a knee is either a "success" or "failure". To obtain a successful result, a knee must reach the 22 + month upper window limit with the device intact and without a component revision/removal or a UADE.
- 4. Radiographic Assessments at the 22+ month assessment

This is a binary endpoint in which a knee is either a "success" or "failure". To obtain a successful radiographic endpoint, a knee must meet the following criteria at the 22+ month

- a. Absence of osteolysis
- b. No migration/subsidence of any femoral or tibial component
- c. Absence of fractured component

Conversely, a radiographic failure is defined as follows:

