3.1 STUDY SUCCESS AND TEST OF THE STUDY'S PRIMARY HYPOTHESIS

This study is designed to show that the investigational device (Cementless) is non-inferior to the Control device using four co-primary study endpoints. This will be shown using a closed testing method in which each of the primary endpoints specified above are compared using α =0.05. Study success requires that the Cementless group successfully demonstrate non-inferiority when compared to the Control group for all four of the individual primary endpoints, using the statistical methods described below. Because non-inferiority must be successfully shown for all four endpoints for study success, the type I error rate is preserved at 5% for the entire primary endpoint.^b The individual non-inferiority hypotheses for each of these four tests are as follows:

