3.4.2. INTENT TO TREAT (ITT) POPULATION

Patients who have met the Inclusion/Exclusion criteria, signed the Informed Consent, and been randomized comprise the ITT population and will be tracked. Those patients that have "fallen out" of the study and did not receive either the investigational or the control device will be summarized by specific reason for not receiving the study device. The primary endpoint will be analyzed for the ITT Population as a sensitivity analysis, with the purpose of evaluating the impact of protocol deviations and missing data on the primary endpoints.

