	into the trial. Six week follow up radiographs will serve as baseline for radiographic endpoints.
Intervention	Randomization will be performed with the use of a validated electronic system under the control of the Sponsor to ensure strict adherence to the protocol.
Follow Up	Mechanisms are in place to ensure that a high degree of subject compliance is maintained. Exclusion criteria have been designed to increase the likelihood of follow up by limiting disease states and other conditions that may interfere with the proposed follow up time period. The minimum duration of follow-up is two years. This is sufficient to capture anticipated effectiveness and to accurately estimate the rate of known or suspected adverse events. The duration of follow-up is identical for study and control populations.
Collection and Validation of Data	Validated methods for capturing data are currently in place and will be monitored for compliance throughout the trial.
Validation of Assumptions	Assumptions made for statistical methods will be checked before beginning a detailed analysis using these methods. If assumptions are not met, more appropriate tests will be used (e.g. non-parametric methods).
Hypothesis and Statistical Tests	The protocol clearly states the hypotheses to be tested and statistical tests to be used.
Pooling	Pooling is justified based on inclusion/exclusion criteria and adherence to the protocol will be strictly monitored and enforced to further justify pooling of study data.
Intent-to-Treat Analysis	An analysis of patients by the assigned treatment will be conducted in the sensitivity analyses for this study.

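### The primary analysis counts a switched knee under the device implanted, and the assigned-arm analysis has no part in the success rule: a small, cheaply closed route to bias

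*Combined protocol and SAP*

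**What the plan says.** Section 3.5.2 bases the primary analysis on the Per Protocol population. For a patient who did not receive the assigned device, "the primary analysis will use the device that was actually implanted if it was a study device"; a patient who received no study device is left out. Section 3.5.4 carries the same rule to the secondary outcomes.

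Section 3.1 sets the success rule: "Study success requires that the Cementless group successfully demonstrate non-inferiority when compared to the Control group for all four of the individual primary endpoints". It adds that, because all four must pass, "the type I error rate is preserved at 5% for the entire primary endpoint". It does not mention assigned arm or intention to treat.

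Section 3.4.2 defines the ITT population as eligible, consented and randomised patients, and says: "The primary endpoint will be analyzed for the ITT Population as a sensitivity analysis". The stated aim is to see how far deviations and missing values affect the results. Appendix B confirms this: "An analysis of patients by the assigned treatment will be conducted in the sensitivity analyses for this study".

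On how often switching may occur, section 3.5.2 gives no figure but says that "it is expected that few patients will fail to receive the assigned treatment". Section 3.0 says that the assignments are in "envelopes to be opened intra-operatively after the first tibial cut and bone quality is assessed against the eligibility criteria".

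**The concern.** Grouping by implanted device keeps the randomised comparison only if switching is unrelated to risk. A cementless-assigned knee that receives cement and then fails is removed from the cementless failures and added to the control failures. Both moves favour non-inferiority. The surgeon knows the assignment once the envelope is open (Appendix B says that double blinding cannot be undertaken), so a switch need not be random.

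The 5% statement in section 3.1 is correct for what it covers, which is multiplicity across four endpoints that must all pass. It does not cover regrouping after randomisation. The analysis that would expose a regrouping effect is planned, but a trial could succeed on the implanted-device result while missing a margin by assigned arm.

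**Working it through.** **The plan's own figure.** Section 3.3 uses 95% success in both arms, a margin of 0.08, one-sided 5%, 90% power and 2:1 allocation, and gives 191 v 96 knees. At those numbers the standard error is √[0.95 × 0.05 × (1/191 + 1/96)] = 0.02727, and Wald power is Φ(0.08/0.02727 − 1.645) = Φ(1.289) = 90.1%. Inflation reproduces too: 191/0.75 = 254.7 and 96/0.75 = 128, giving 255 and 128. The sample size is not in question.

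**How two switches can split the analyses.** The counts are assumed. The test passes if (p_C − p_I) + 1.645 √(SE_C² + SE_I²) is 0.08 or less (sections 3.1.1 and 3.2).

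- By assigned arm, failures 5/96 control and 16/191 cementless: difference 0.0317, upper bound 0.0815. Not shown.
- Two cementless-assigned knees received cement and both failed, so as planned 7/98 v 14/189: difference 0.0026, upper bound 0.0557. Shown.

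**Type I error, radiographic endpoint.** Inputs from the documents: 255 and 128 knees less 15% attrition (255 × 0.85 = 216.75, 128 × 0.85 = 108.8, so 217 v 109), control failure 5%, margin 0.08. Assumed: m cementless-assigned knees receive cement, and knees are independent. The results come from exact enumeration of three binomial counts (unswitched cementless, switched, control).

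*Scenario A: true failure by assigned arm is 13% v 5%, exactly at the margin.* Switched knees fail at rate r, and unswitched cementless knees at (217 × 0.13 − m r)/(217 − m). With no switch the error is 0.0440. Under the planned grouping:

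| m | r = 5% | r = 10% | r = 20% | r = 30% |
|---|---|---|---|---|
| 1 | 0.0459 | 0.0480 | 0.0525 | 0.0572 |
| 2 | 0.0442 | 0.0484 | 0.0575 | 0.0676 |
| 7 (7/217 = 3.2%) | 0.0379 | 0.0519 | 0.0907 | 0.1458 |

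The planned analysis passes while the assigned-arm analysis fails in 0.2-2.6% of trials with 1-2 switches. If the assigned-arm analysis must also pass, the error is 3.1-4.4% across m = 1 to 7 (for m = 2, r = 30%: 0.0418). It cannot exceed the assigned-arm error, which this scenario fixes at the margin.

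*Scenario B: the 8-point deficit is the device effect had every knee received its assigned device.* Switched knees have k times the risk of the others on either device. With w = m/217, the others fail at 0.13/(1 − w + wk) on cementless and 0.05/(1 − w + wk) on cement. For m = 2, k = 6: w = 0.0092, and switched knees on cement fail at 6 × 0.05/1.046 = 28.7%. The planned error is 5.4% (m = 1, k = 3), 6.1% (m = 2, k = 3) and 8.7% (m = 2, k = 6). Requiring the assigned-arm analysis as well lowers the last to 5.6%. At the extreme of m = 7, k = 6, the planned error is 24.2%, falling to 9.8%. Some inflation remains because the switches themselves dilute the assigned-arm difference.

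*Control knees given cementless, scenario A.* If switched knees fail at 13%, the average on cementless in this scenario, the planned error is 4.1%, 4.1% and 3.7% for 1, 2 and 4 knees; at 30% it is 3.5%, 2.9% and 1.8%. If they are low risk it rises: at 5%, 4.5%, 4.7% and 5.1%; at 2%, 5.7% for 4 knees.

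All these are errors for one endpoint. Study success needs all four, so the chance of a false study success is no higher.

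**The case against.** The strongest reply is that the plan already settles which result decides. One analysis is called primary and the other sensitivity, and the success rule is tied to the primary endpoints. That stands. A reader might infer that the hierarchy is undefined, or that an ITT analysis is missing; the documents support neither. The only explicit rule for disagreeing sensitivity analyses (section 3.5.5) needs more than 15% missing values and offers optional multiple imputation, which does not address switching. But the labels still imply that the as-treated result prevails. The remaining concern is that this result decides alone.

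The second reply is that the harm is hypothetical. No switch rate is given, and few switches are expected. Bone is assessed before the envelope is opened, which removes much of the route from poor bone to a switch. With one or two switches, clear inflation in scenario A needs switched knees to fail at 20-30%, four to six times the planned 5%. This also stands and keeps the severity low.

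Two further inferences are tempting. One is that switching from control to cementless is always conservative; the low-risk figures show otherwise. The other is that switched knees must be excluded from the primary set. Once the assigned-arm analysis is required, exclusion adds no error control for cementless-to-cement switches (m = 2, r = 30%: 0.0437 with exclusion, 0.0418 with the planned grouping kept).

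**Conclusion.** The concern holds in a limited form. The planned primary analysis is as-treated, and the assigned-arm analysis has no role in the success rule. With one or two cementless-to-cement switches, the radiographic type I error is 4.4-6.8% in scenario A, against 4.4% with no switching. It can reach 8.7% in scenario B with two switches at six times the risk. Switching the other way is conservative when the switched knees are at average or higher risk, but not when they are low risk.

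Every switch count, failure rate and risk ratio for switched knees is an assumption, and only the radiographic endpoint was examined. A reader might infer that the 5% statement in section 3.1 is wrong or that the trial's error rate is known to be inflated. The documents support neither: the statement concerns multiplicity, and the expected number of switches is small. This is a cheap improvement, not a fatal flaw.

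**What to change.** In section 3.1, state that non-inferiority on each endpoint also requires the analysis by assigned arm to meet the same margin. Specify that this analysis:

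- uses randomised patients who received either study device, and is therefore narrower than the ITT population of section 3.4.2;
- follows the same missing-data rules as the primary analysis;
- places a non-randomised second knee (note to section 2.2) in the patient's assigned arm.

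The implanted-device grouping in sections 3.5.2 and 3.5.4 can stay. Excluding switched knees is optional and is justified only by power when control knees receive cementless.

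Cost: no new data and little extra analysis. With 5% radiographic failure in both arms and 1-7 cementless-to-cement switches, power is 94.7-95.9%, against 95.7% by assigned arm. With 1-4 control knees given cementless, power is at most about 1 point below the planned rule, which itself gives 89.3-95.9% there. Power for the other three endpoints, and jointly, is not quantified; the documents as shown give no standard deviations for the Knee Scores. Because the success rule changes, section 2.13 calls for IRB or EC approval and, if necessary, FDA approval.

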- 24. Patients who have received systemic steroids within the past 6 months or steroid injection into the affected knee within the previous 6 weeks prior to enrollment
- 25. Patients who are pregnant
- 26. Patients with severe valgus or varus knees (valgus or varus angulation of more than 20°) where collateral ligament, iliotibial band, or popliteal release is required
- 27. Patients who refuse to sign the IRB approved Informed Consent Form
- 28. Participation in an interventional clinical research study procedure, *other than a bilateral knee arthroplasty in this study*, within the past 12 months
- 29. Patients with a history of osteomyelitis or sepsis of the index knee
- 30. Patients who require patellar resurfacing
- 31. Patients who are not skeletally mature
- 32. Patients who have had a total hip replacement procedure <18 months prior to entering the study
- 33. Patients who have had a contralateral non-study knee replacement procedure <18 months prior to entering the study
- 34. Patients who are found intraoperatively to have inadequate bone stock or other conditions that contraindicate a partial knee replacement

NOTE: Patients implanted on the contralateral knee with the investigational or control device as part of their participation in the study are permitted to be enrolled in the study, but will receive a matching device to the original study knee and will not be randomized.

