 - A life-threatening event is one where the patient is in immediate danger of death unless intervention is done. It does not mean that the patient may die at some time in the future from the event or may have died if the event had been more serious or specific.
- Requires in-patient hospitalization or prolongation of existing hospitalization
 - A planned hospitalization for a pre-existing condition, or a procedure required by the clinical investigation plan, without a serious deterioration in health is not considered to be a serious adverse event.
- Results in persistent or significant disability/incapacity
 - A significant disability is one that causes substantial disruption to the person's normal life and activity.
- Results in a congenital anomaly/birth defect.

Staged Bilateral: Any contralateral study knee replacement performed during the course of the study, but not under the same course of anesthetic

Unanticipated Adverse Device Event (UADE): Unanticipated adverse device effect is any serious adverse effect on health or safety or any life-threatening problem or death caused by or associated with this device, which was not previously identified in nature, severity, or degree of incidence in the application of the device or any other unanticipated serious problem associated with a device that relates to the rights, safety, or welfare of subjects.

If the complication is characterized as an "unanticipated adverse device effect," the investigator will submit a detailed report to Sponsor and the reviewing IRB/EC immediately, but in no event later than ten (10) working days after the investigator first learns of the effect, per 21 CFR 812.150(a)(1). Sponsor, in turn, is required to submit a report to the FDA, all reviewing IRB/ECs, and participating investigators within ten (10) working days.

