2.11 PRIMARY AND SECONDARY STUDY ENDPOINTS

The study's primary safety and efficacy endpoints for the Oxford® Cementless Partial Knee System will include:

• Radiographic Success at 22+ months Study ID: ORTHO.CR.US30

- Absence of Revision/Removal/UADE at any time point
- The Knee Society Assessment Score at 22+ months
- The Knee Society Function Score at 22+ months

The study's secondary endpoints include:

- The Knee Society Assessment Score at all time points other than 22+ months
- The Knee Society Assessment Score for bilateral subjects at all time points
- The Knee Society Function Score at all time points other than 22+ months
- The Knee Society Function Score for bilateral subjects at all time points
- The Oxford Knee Score at all time points
- Radiographic Success at all other time points
- Single question assessment of patient satisfaction at all time points^a

The safety of the system will further be monitored by recording and reporting adverse events [including serious adverse events not considered UADEs throughout the follow-up period].

Safety data will be summarized as follows:

- Device removals or revisions
- Unanticipated adverse device events
- Systemic adverse events
- Local adverse events
- Reoperations and Other Interventions

Any patient who fails to return for multiple, consecutive, scheduled follow-up visits for any reason other than the criteria listed above will be identified as Missing Data.

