3.1.5. SENSITIVITY ANALYSES - UNILATERAL AND BILATERAL KNEES

To address the impact of possible correlation occurring due to including two knees from the same patient, for the two endpoints that will incorporate bilateral knees (Radiographic Success and Absence of Revision/Removal/UADE), additional sensitivity analysis will be conducted in order to address any potential correlation occurring due to including two knees from the same patient. These are to include:

- a. An analysis that considers only unilateral subjects.
- b. A repeated measures model approach that can account for possible correlation within subjects.
- c. An analysis of data at the patient level, in which a patient is considered a "failure" if either knee fails.

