3.5.4. Analyses of Secondary Outcomes

These outcomes include the primary study endpoints at times other than two years. In addition, a composite success/failure endpoint consisting of the four primary outcomes will be tested for non-inferiority, Cementless vs. Control, using a non-inferiority margin of 10%. In this composite, the threshold for success for the Knee Society Assessment and Function scores will be 80 points. A composite success outcome requires a successful outcome for all four components.

In addition, at all-time points, implant revisions or removals will be described by Kaplan-Meier time-to-failure curves and compared using log-rank tests. Mean Knee Society Assessment Score, Knee Society Function Score, and Oxford Knee scores will be displayed by time point and compared between treatment groups. Analyses will be performed using standard statistical tests and will be chosen as appropriate for the scale and distribution of

the measures being analyzed (chi-square, Cochran-Mantel-Haenszel chi-square, Student's t).

Bilateral patients will be analyzed as a separate group for purposes of secondary analyses of Knee scores at each time point as well in the secondary analysis of composite success rates. For other analyses, including radiographic and safety outcomes, bilateral and unilateral patients will be analyzed together.

Secondary outcomes will be analyzed using all patients with available data for the endpoint being analyzed. As with the primary analysis, the secondary analyses will use the device that was actually implanted if it was a study device; if a study device is not received, the patient will not be included in the secondary analyses.

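### The primary knee-score tests exclude staged bilateral patients on a post-randomisation event, and no planned sensitivity analysis clearly restores their randomised first knees

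*Combined protocol and SAP*

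**What the plan says.** Section 3.0 sets the unit of allocation: "Randomization will be per patient". The note closing section 2.2 says that a patient who later has the other knee done in the study "will receive a matching device to the original study knee and will not be randomized". Section 2.5 defines a staged bilateral as "Any contralateral study knee replacement performed during the course of the study, but not under the same course of anesthetic".

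Section 3.5.2 keeps bilateral patients in the two binary co-primary analyses but not in the knee-score ones: "The bilateral patients will not be included in the primary analysis for the Knee Score endpoints". The reason given is that one knee may influence the score of the other. The rule applies to the whole patient and does not say when bilateral status is determined.

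The scores are not discarded. Section 3.5.2 adds that these patients stay in the binary analyses "but will be analyzed separately for the Knee Society Function and Assessment endpoints". Section 2.11 lists as a secondary endpoint "The Knee Society Assessment Score for bilateral subjects at all time points", with a matching entry for Function. Section 3.5.4 says: "Bilateral patients will be analyzed as a separate group for purposes of secondary analyses of Knee scores at each time point". Section 3.5.6 examines device group against each primary endpoint by unilateral or bilateral status, and uses that status as a regression covariate. The sensitivity analyses in section 3.1.5, however, are "for the two endpoints that will incorporate bilateral knees (Radiographic Success and Absence of Revision/Removal/UADE".

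**The concern.** A staged patient enters the trial with one randomised knee and contributes to the knee-score comparison until a second study knee is implanted. From then on, the rule takes the first knee out of both primary knee-score tests. If the decision to have a second knee done in the study is related to how the first knee fared, the patients who remain are a selected set in each arm, and randomisation no longer protects the comparison. Section 3.5.1 treats unilateral or bilateral status as a baseline characteristic, which for staged patients it is not.

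Section 3.1 requires all four endpoints to succeed and argues from this that the overall error stays at 5%. That argument needs each individual test to hold its own 5%. Bias towards non-inferiority in a knee-score test weakens it.

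**Working it through.** **1. The plan's own numbers.** Inputs from section 3.3: success 0.95 in both arms, margin 0.08, one-sided alpha 0.05, power 90%, allocation 2:1.

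- Control n = (1.645 + 1.282)² × (0.0475 + 0.0475/2) / 0.08² = 8.56 × 0.07125 / 0.0064 = 95.3, so 96. Cementless is about twice that. The plan states 191 and 96. The Farrington–Manning form that it names gives 188 and 94, within 3%.
- Inflation: 287 / (1 − 0.10 − 0.15) = 382.7, so 383. This matches the plan.

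The 10% allowance therefore covers the loss of numbers if about 10% of patients are bilateral. It does nothing about who is lost.

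**2. Which planned analyses put the first knees back into an arm-level comparison?**

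- Section 3.1.5: binary endpoints only.
- Separate bilateral analyses (sections 2.11, 3.5.2, 3.5.4): a different group, not the randomised whole. At 10%, it is about 26 v 13 of 255 v 128 before attrition.
- Section 3.5.6: exploratory. Its regressions adjust for bilateral status, which is itself the post-randomisation variable.
- Section 3.4.2 (ITT sensitivity analysis): includes all randomised patients but does not say whether bilateral knee scores re-enter.

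**3. Size if staging depends on the first-knee score, with the same rule in both arms.** No SD is given. The assumed SD is 17.5, the largest at which 191 v 96 gives 90% power for the 6.4-point margin: 6.4 / [2.926 × √(1/96 + 1/191)] = 17.5. Scores are taken as normal with a true Control minus Cementless difference of 6.4. The probability of staging is logistic in the first-knee score, with slope b per SD and the intercept set to give the assumed overall share at 2:1. The retained mean in each arm is the average score weighted by (1 − probability of staging). Bias is 6.4 minus the retained difference. SE = 17.5 × √(1/96 + 1/191) = 2.19, and error = Φ(−1.645 + bias/SE).

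| Staged share | b | Retained difference | Bias towards non-inferiority | One-sided error |
|---|---|---|---|---|
| 5% | +0.5 / −0.5 | 6.33 / 6.33 | 0.07 / 0.07 | 5.4% / 5.3% |
| 5% | +1.0 / −1.0 | 6.13 / 6.16 | 0.27 / 0.25 | 6.4% / 6.3% |
| 10% | +0.5 / −0.5 | 6.26 / 6.27 | 0.14 / 0.13 | 5.7% / 5.7% |
| 10% | +1.0 / −1.0 | 5.94 / 5.97 | 0.46 / 0.43 | 7.6% / 7.4% |

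Both signs of b shrink the difference. If good first knees lead to a second, the better arm loses more of its high scores. If poor first knees do, the worse arm loses more of its low scores.

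**4. Size if staging rates differ between arms for other reasons.** If staged patients score g points lower than the rest, dropping them shifts Control minus Cementless by (fC − fI) × g, where f is the staged share in each arm.

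- Equal shares: 0.
- 5% v 10%, g = 10: −0.5 points, or 8% of the 6.4 margin.
- 5% v 15%, g = 20: −2.0 points, or 31%.
- Swapping the arms reverses the sign.

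**5. How many 22+ month scores would predate a second operation?** Section 2.0 gives about three to five years in total, ending at the last patient's 2-year visit. That leaves roughly one to three years (T) for implanting study knees. If both operations fall independently and uniformly over T months (an assumption), the share of pairs more than 22 months apart is (1 − 22/T)²: none at T = 12, (2/24)² = 0.7% at 24, and (14/36)² = 15% at 36. With 10% staged, that is at most about 1.5% of patients.

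**The case against.** The exclusion is prespecified, identical in both arms, budgeted in the sample size and supported by a stated reason. For simultaneous bilateral patients, status is normally settled by the index surgery, so the criticism does not reach them. All of this stands.

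A reader might infer that staged patients vanish from every knee-score analysis, or that no planned analysis contains all randomised patients. The documents do not support either. Bilateral scores are secondary endpoints at every visit, and the section 3.5.6 models need them in order to fit bilateral status as a covariate. Appendix B confirms an analysis by assigned treatment, and section 3.4.2 does not exclude them. The most that can be said is that no planned analysis clearly restores the randomised comparison.

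A reader might also see the main harm in discarding 22+ month scores taken before the second operation. The stated reason cannot apply to an implant not yet in place, and the rule read literally does move those scores to the separate group. But step 5 shows that few patients would be concerned, so a timing rule alone would remove little of the bias.

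Finally, a bias of about 0.7 points needs 20% staged and the steepest slope. The plan's 10% allowance covers simultaneous and staged patients together, so 5 to 10% staged is the fairer range.

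**Conclusion.** The point holds for staged bilateral patients in the two primary knee-score tests. Their inclusion depends on a post-randomisation event, with no timing rule and no sensitivity analysis that clearly brings back their first knees. The likely effect is modest: about 0.07 to 0.46 points, or 1 to 7% of the 6.4-point margin, with one-sided error of about 5.3 to 7.6%. This rests on an assumed SD of 17.5, a true difference at the margin, 5 to 10% staged, a common selection rule and log-odds slopes of 0.5 to 1.0 per SD. The documents supply none of these. A general claim of bias towards non-inferiority is not supported: if staging rates differ between arms for other reasons, the sign depends on which arm has more second operations. The change is worth making because two of the four tests needed for study success are affected and the data are already collected.

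**What to change.** Extend section 3.1.5 to the Knee Society Assessment and Function scores. For each, prespecify a sensitivity analysis of the randomised first knee of every unilateral and staged bilateral patient, by assigned device, against the same margin (6.4 or 9.2 points). Report it beside the unilateral-only primary result. Say in section 3.4.2 that these first-knee scores are included in the ITT analysis.

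Also state in section 3.5.2 that a 22+ month first-knee score recorded before the second surgery stays in the primary analysis. This concerns few patients but aligns the rule with its stated reason.

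The cost is SAP wording and one added analysis per score, with no new data. The downside is that scores taken after a second surgery may carry some influence from the other knee. That is confined to the sensitivity analysis, and the unilateral-only result beside it lets a reader judge it.
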